3.0 Purpose

The purpose is to evaluate the safety and effectiveness of Mobility+ enteral feeding system via this initial post-market study (510k clearance number K222678) in adults, a subset of the intended use population. This evaluation will be conducted in a prospective, single arm, non-randomized clinical study.

Hypothesis and Objectives

The study hypothesis is that Mobility+ meets its intended use, safely. The objectives are to evaluate the below primary and secondary endpoints, through execution of this protocol:

Endpoint	Detail	How it will be measured
Primary: Safety and Effectiveness of Mobility+	Evaluate participants who have received familiarization training can use device, according to IFU, to allow delivery of liquid nutrition to their feeding tube, in a real-life setting (home), safely (i.e. can execute critical device use tasks to allow feeding, without serious adverse events) and with effectiveness (i.e. using Mobility+ for the majority or all of their feeding sessions i.e. two daily feeds, minimum)	Phone communication and checklist (Appendix8)

Secondary: Usability of Mobility+	Evaluate Participant perspectives on mobility, ease of use and tolerance, with their current feeding system(s) and Mobility+	Participant perspectives surveys: Baseline (Appendix 4) End of study (Appendix 7)
	Evaluate changes in participant Quality of Life (QoL)	QoL survey at baseline (Appendix 5) and QoL question at end of study (Appendix 7)
	Estimate if participants consume similar average volume (and kcals) of feed/day during the study, compared to baseline	Collect descriptive data on estimated average feed volume and kcals consumed at baseline (Appendix 3) and at end of study (Appendix 8)

The outcome will be presented in a study report.

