effect (SAE)	
 a) Death b) Serious deterioration in the health of the subject, users, or other persons as defined by one or more of the following: 
 1) A life-threatening illness or injury, or 2) A permanent impairment of a body structure or a body function including chronic diseases, or 3) In-patient or prolonged hospitalization, or 4) Medical or surgical intervention to prevent life-threatening illness or injury, or permanent impairment to a body structure or a body function, c) Fetal distress, fetal death, a congenital abnormality, or birth defect including physical or mental impairment
Adverse device effect (ADE)	Adverse event related to the use of an investigational medical device.
Serious adverse device effect (SADE)	Adverse device effect that has resulted in any of the consequences characteristic of a serious adverse event
Unanticipated serious adverse device effect (USADE)	
Serious adverse device effect which by its nature, incidence, severity or outcome has not been identified in the current risk assessment
 
Note: Anticipated serious adverse device effect (ASADE) is an effect which by its nature, incidence, severity or outcome has been identified in the risk assessment

Serious public health threat	Serious public health threat, means an event which could result in imminent risk of death, serious deterioration in a person's state of health, or serious illness, that may require prompt remedial action, and that may cause significant morbidity or mortality in humans, or that is unusual or unexpected for the given place and time
Stock-Keeping Unit (SKU)	A Stock-Keeping Unit is a number (and sometimes letters) that is assigned to a product for the purpose of inventory management and ease or tracking

	
Safety and Effectiveness of A Novel Enteral Feeding System: Prospective Study Protocol Page 13 of 49
	
NCT06173063

---	---	---

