8.11 Phone Communication

1. Pre-intervention phase – Trial days

Phone communication on **Trial Days 1; 3 and 5**: Participant is contacted by telephone to ensure the participant is becoming familiar with using the device including the most appropriate giving-set tubing SKU. (**Appendix 6**).

2. Intervention phase – Study days

- Phone communication - Study **Day 7**: Participant is contacted by telephone to ensure they are successfully and safely feeding with an appropriate tubing SKU, and check compliance and calorie intake (**Appendix 8**).
- Phone communication -Study **Day 14**: Participant is contacted by telephone to ensure participant is successfully and safely feeding with an appropriate tubing SKU, and check compliance and calorie intake. Operator also evaluates self-perceived wellbeing, mobility, wearing methods, and longer-term device use wishes (**Appendix 8**) Administer participant perspectives outcome survey, including question on QoL (**Appendix 7**)

Note: Regarding disposal – as per IFU, devices are disposed of alongside normal waste.

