Trial Day 5: SKU that participant is using: 
 
 440mm RED 	700mm BLUE 	1000mm GREEN 	1900mm WHITE 	
 
					440mm RED 	700mm BLUE 	1000mm GREEN 	1900mm WHITE 
440mm RED 	700mm BLUE 	1000mm GREEN 	1900mm WHITE 					
Select one: 		Stay on this SKU 						
		Trial _____ SKU 						
Reason for changing: <hr/>								
Have you been admitted to hospital in the last 5 days/during this trial period?		 Yes		 No				
Note to operator: Confirm you have reminded participant of the day they will begin the 14 day study period		 Yes		 No				

Appendix 7

Participant perspectives outcome survey

Participant perspectives of Mobility+ feeding system: Usability, mobility, and ease of use, including general end of study questions

(Operator asks the Participant these questions)

During use of the Mobility+ system, how do you find these activities?		Very Difficult	Difficult	Neutral	Easy	Very Easy
Moving from one room to another room						
Going up and down stairs						
Short walk (e.g., one block)						
Long walk (e.g., several blocks)						
Travelling in car/public transport						
Moderate intensity physical activities, such as:						

 - Moving a table - Pushing a vacuum - Bowling - Playing golf 						
Other daily activities (e.g., lifting or carrying groceries, household chores)						
Ability to sleep						
Socializing with friends/family						
During use of the Mobility+ system, how did you find working/studying or both? Please log N/A if participant does neither	Very Difficult	Difficult	Neutral	Easy	Very Easy	N/A
Note to operator: When scoring this questionnaire, assign points using the legend below.						
Very Difficult = 0 points, Somewhat Difficult = 1, Neutral = 2, Somewhat Easy = 3 and Very Easy = 4						
Thinking about your overall						

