experience with the Mobility+ system, how strongly do you agree or disagree with the following statements?	Strongly Disagree	Some-what Disagree	Neutral	Some-what Agree	Strongly Agree
The Mobility+ system is easy to use					
The Mobility+ system is easy to carry					
The silent nature of The Mobility+ system during use is acceptable					
The Mobility+ allows me to feed discreetly					
I am satisfied with the overall performance of the Mobility+ system					
Note to operator: When scoring this questionnaire, assign points using the legend below. Strongly Disagree = 0 points, Somewhat Disagree = 1, Neutral = 2, Somewhat Agree = 3 and Strongly Agree = 4					
Do you experience any of the following symptoms of feed intolerance while on your current feeding system?					
Gas/Bloating?	□ Yes			□ No	
If yes, is it mild, moderate, or severe?	Mild □	Moderate □	Severe □		
Abdominal Pain?	□ Yes			□ No	
If yes, is it mild, moderate, or severe?	Mild □	Moderate □	Severe □		
Diarrhea?	□ Yes			□ No	
If yes, is it mild, moderate, or severe?	Mild □	Moderate □	Severe □		
Constipation?	□ Yes			□ No	
If yes, is it mild, moderate, or severe?	Mild □	Moderate □	Severe □		
Nausea/Vomiting?	□ Yes			□ No	
If yes, is it mild, moderate, or severe?	Mild □	Moderate □	Severe □		
Reflux?	□ Yes			□ No	
If yes, is it mild, moderate, or severe?	Mild □	Moderate □	Severe □		
Have you been admitted to hospital since you last received phone communication?	□ Yes			□ No	
General End of Study Questions:					

When answering the following questions, consider how **the last 14 days with Mobility+** have been compared to an average week of using the feeding system that you had **before you started this study**. Please try to answer based **solely on your experience with the Mobility+** in the last two weeks and not on external factors that may have positively/negatively impacted your week of using the Mobility+.

How do you feel your overall Quality of Life has been during the last 2 weeks of using Mobility+?

Excellent	Good	Neutral	Bad	Very Bad
				

How mobile have you been in your everyday activities during the last 2 weeks of using Mobility+, compared to before you started the study?

Much Better	Somewhat Better	About the Same	Somewhat Worse	Much Worse
				

How do you rate the importance of being mobile in your everyday activities to your overall wellbeing?

Very Important	Somewhat important	Not important at all

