		

How strongly do you agree with the following statement? I would like to use the Mobility+ again.

Strongly Agree	Somewhat Agree	Neutral	Somewhat Disagree	Strongly Disagree
				

If you would like to use Mobility+ again, how often would you like to use it?

Every Day	Every Week	Every Month
		

Think about your overall wellbeing if you used Mobility+ for SOME/ALL of your tube feeding needs, in the long term. How would your wellbeing be then, compared to now?

Much Better	Somewhat Better	About the Same	Somewhat Worse	Much Worse
				

Would you pay out of pocket for the Mobility+?

YES	NO
	

How did you choose to wear the Mobility+ system?

- Crossbody bag**
- Handbag**
- Backpack**
- In clothing**
- Clipped onto belt/clothing**
- Other (Detail):**

Appendix 8

Appendix 8 - Phone communication check sheet (Study Day 7 and 14) - (Operator asks the Participant these questions)

Day 7

Day 7			
Questions:	Answers:		
Day 7 Safety & Effectiveness Check			
Are you able to use Mobility+ to successfully and safely provide enteral feeding?	 YES  NO		
Day 7 Compliance & Calorie Intake Check			
Consider your feed intake over the last 3 days (i.e. Study day 4, 5, 6).			
Questions:	Answers:		
What volume of enteral nutrition did you consume on average per day (i.e. over 24 hr)?	Volume Mobility+mls		
How many hours did you typically infuse for, on average/day? hours minutes		
How many feedings did you intend to take using Mobility+ , on average / day?feedings		
How many feedings were you able to take using Mobility+ , on average / day?feedings		
What was the average volume of enteral nutrition that you consumed per feeding with Mobility+?mls		
What time of the day did you provide feedings with Mobility+?	Morning  Afternoon  Evening  Night-time 		
Operator facing question: On average, did the participant take at least two daily feeds with Mobility+? If no, why not?	 YES		
	 NO		
Day 7 Tubing SKU check			
Study Day 7:			
SKU that participant is using:			

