7.0 Supplemental Outcome data gathered

The following supplemental Outcome Data was gathered (n=17).

Compliance and Effectiveness (n (%))	
Successfully and safely feed with Mobility+	17 (100)
Achieved use of Mobility+ for minimum 2 daily EN feeds	16 (94.1)

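### The primary safety component is SAE-free use, but its named checklist, as printed, has no SAE item and neither document specifies an SAE count

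*SAP*

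**What the plan says.** Protocol 3.0 makes safety one half of the primary endpoint. Participants should use the device at home in such a way that they "can execute critical device use tasks to allow feeding, without serious adverse events". The measurement column reads "Phone communication and checklist (Appendix8".

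Appendix 8 is completed on Study Days 7 and 14. On each day its safety item is one yes/no question put to the participant: "Are you able to use Mobility+ to successfully and safely provide enteral feeding". The remaining items concern intake, number of feeds, timing and giving-set tubing.

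Protocol 7.0 lists "In-patient or prolonged hospitalization" among the outcomes that make an adverse event serious. Protocol 8.13 ends a participant's involvement on hospitalization for any reason and cites Appendices 6 and 8 for this. Appendix 6 asks, on Trial Day 5, "Have you been admitted to hospital in the last 5 days/during this trial period". Appendix 7 asks, on Study Day 14, "Have you been admitted to hospital since you last received phone communication".

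Protocol 10.0 and Appendices 9 and 10 require the investigator to record and classify adverse events and to report serious matters within 24 hours. Protocol 8.7 requires withdrawals to be logged with the reason.

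On analysis, Protocol Table 5 (section 11.2) deals with the surveys. SAP 4.0 and 5.0 deal with rating scores and their test. SAP 7.0 gives supplemental outcome data for n=17 under a compliance and effectiveness heading. Its first row is "Successfully and safely feed with Mobility" (plus sign omitted), 17 (100).

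**The concern.** The endpoint is defined by an event, whereas the instrument named for it asks for an opinion about present ability. Someone who had an SAE and recovered could truthfully answer yes. Someone admitted to hospital is withdrawn and is no longer due the later calls. A result built only on the checklist could therefore read 100% whether or not a device user had an SAE.

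What is at stake is the meaning of the study's main safety statement. From the row alone, a reader cannot tell whether no device user had an SAE, or whether no one who answered the question reported a problem. Neither document fixes which SAEs count towards the endpoint, or in whom.

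**Working it through.** The question is mainly one of setting the texts side by side. The little arithmetic concerns denominators.

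1. **What the endpoint needs.** For each device user, whether an SAE occurred (Protocol 3.0, with the SAE definition in 7.0).

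2. **What each source supplies.**
   - Appendix 8, Study Days 7 and 14: self-reported ability to feed. No SAE or admission item is printed, although 8.13 cites this appendix for the hospitalization stop.
   - Appendix 6, Trial Day 5: admission during the trial period.
   - Appendix 7, Study Day 14: admission since the previous call. Section 3.0 assigns this survey to the secondary endpoints.
   - Section 10.0 and Appendices 9 and 10: investigator-classified SAEs.
   - Section 8.7: withdrawals with reasons.

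   Only the first is named as the checklist for the primary endpoint. The fourth holds the defining event directly, and nothing links it to the endpoint.

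3. **What the analysis text supplies.** Table 5 covers the perspectives surveys, quality of life and the general end-of-study questions. SAP 4.0 scores mobility, ease of use and quality of life. SAP 5.0 names a paired t-test with ANOVA. None specifies an SAE count or a safety population.

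4. **Who can appear in a checklist row.** Take a hypothetical participant admitted on Study Day 3. Under 8.13 participation stops, so neither Appendix 8 call is due. If the row counts those who answered, this person is in neither numerator nor denominator, and the row can still read 100%.

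5. **Reproducing the SAP's figures.** Included: 548 − 493 − 11 − 25 = 19 (SAP 3.0). Tabulated: 17 (SAP 6.0 and 7.0). Not tabulated: 19 − 17 = 2, with no explanation. The SAP 7.0 percentages reproduce on 17: 17/17 = 100% and 16/17 = 94.1%.

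6. **What a true zero would support.** This is illustrative only, as no SAE count is given. The exact two-sided 95% upper limit for 0 of n is 1 − 0.025^(1/n). For n = 17 it is 19.5%, and for n = 19 it is 17.6%.

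That the row comes from Appendix 8 is an inference from the similar wording. The SAP names neither its source nor its day.

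**The case against.** The strongest reply is that the measure is a phone call plus a form, not one tick box. Protocol 8.13 makes the calls a route by which adverse events become known. The Day 14 call also includes the instruction "Administer participant perspectives outcome survey, including question on QoL", and that survey (Appendix 7) contains an admission question. Table 3 even lists the end-of-study safety check under Appendix 7. The missing Appendix 8 item may be a loose cross-reference or a row lost from the printed form, and the electronic forms cannot be seen. SAEs are defined, classified and promptly reported. SAP 7.0 is supplemental and does not claim to report the SAE component. The study report and the sponsor's procedures may handle the count.

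Much of this stands. It would be wrong to say that SAEs are not collected, and the point is confined to these two documents. But even with Appendix 7 included, its answers come only from those still reached on Day 14. Neither document says that its admission item, or the investigator's SAE records, decides the endpoint.

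A reader might draw two stronger inferences, and the documents support neither:

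- **That SAEs in some weeks would be missed.** Read literally, the two admission questions do not cover Trial Days 6–7 or Study Days 1–6. That describes question wording, not lost events: an admission on those days ends participation, withdrawals are logged with reasons, and the investigator must report serious matters within 24 hours.
- **That the two participants not tabulated were device users with SAEs.** The baseline table, described as gathered at enrollment, also has n=17. This allows that they never started the device. Nothing gives their reason for leaving.

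**Conclusion.** The point holds as a gap between the endpoint's definition and its specified measurement and analysis. Followed as printed, the Appendix 8 item cannot detect the event that defines the safety component, and no rule brings in the records that can. The 17 (100) row therefore does not by itself establish that component.

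No numerical size can be attached. The documents contain no SAE result, and nothing shows the row to be wrong. The conclusion rests on Appendix 8 being complete as printed and, for its bearing on SAP 7.0, on the row being drawn from that checklist. If the row instead came from the investigator's SAE records, the remaining defect would be an unstated source and population. For a small single-arm study of a cleared, low-risk device this should be corrected, but it does not invalidate the study.

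**What to change.** In the SAP, define the safety component as the number and percentage of participants with at least one investigator-classified SAE (section 10.0 records) among everyone who used the device from Trial Day 1. Cross-check that count against the admission answers in Appendices 6 and 7 and against the withdrawal log. The log is needed because the two admission questions do not span the whole period of use. An exact confidence interval is optional.

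If Appendix 8 is the source of the present SAP 7.0 row, label the row as participant-reported and give its day. State whether the two of 19 not tabulated used the device, and why they left.

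The cost is a one-line definition, one reported count, a row label and a sentence on the two participants. All of it comes from records the protocol already requires, with no new data collection. The downside for the sponsor is that the safety result may look less favourable than 17 (100). If the count is zero, the safety statement becomes stronger than the present row allows.
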